9.3.4 Removal of Patients from the Study

Patients will be advised that they are free to withdraw from the study at any time for any reason or, if necessary, the Investigator may withdraw a patient from the study to protect the health of that patient. A patient may also be withdrawn for not complying with study procedures. The clinical report will include all reasons for early withdrawals.

CONFIDENTIAL PROTOCOL

An Open Label, Safety Study to Assess the Potential for Adrenal Suppression Following Maximal Use Treatment with Desoximetasone 0.25% shampoo(Taro Pharmaceuticals U.S.A., Inc.) in Patients with Scalp Psoriasis

All patients who administer at least one dose of randomized study medication will be included in the safety analysis. If a patient terminates from the study early, all efforts will be made to complete their next visit study procedures. In case of early termination the Investigator shall fully document the reason for early termination. Reasons for early termination may include the following:

- Patient withdrew consent
- Significant adverse event that led the Investigator or patient to withdraw for safety reasons
- Worsening signs/symptoms of scalp psoriasis
- Development of an intercurrent condition or complication that could affect the safety of the patient or the validity of the evaluation of the patient's clinical state to an extent considered significant by the Investigator
- Signs and symptoms of possible HPA axis suppression
- Protocol deviations/violations that in the Investigator's opinion warrant discontinuation

Non-compliance with dosing need not be a reason for early termination. Patients who withdraw or are removed from the study will not be replaced. In the event a patient withdraws or is dropped from the study for any reason, the Investigator will request return of the unused product and report the reason for the discontinued participation.

When a patient discontinues early from the study, all study procedures required for the end of study should be performed at their last study visit. Patients who are discontinued from the study will be evaluated for safety and will be given, or referred for, appropriate treatment.

9.4 Treatments

9.4.1 Treatments Administration

The patient will be instructed to apply the study product to psoriasis-affected areas of the dry scalp once daily for 28 days. Patients are to move the hair away from the dry scalp so that one of the affected areas is exposed. A small amount of the study shampoo is to be applied directly to the affected area by gently squeezing the bottle. The shampoo is to be gently rubbed into the affected area. The same procedure is to be followed for other affected areas on the scalp. Patients will be instructed to use only enough to cover affected areas and avoid application to face, groin, armpits, lips or eyes. If during application the product comes in contact with the eyes or eyelids, patients will be instructed to rinse the area with abundant water immediately. Patients should not cover the head with a shower cap while the shampoo is on the scalp. The shampoo is to be left in place for 15 minutes before adding water, lathering and rinsing hair and scalp completely.

The patient will be instructed to apply the medication once daily until the patient's next scheduled visit. Each patient will be provided with a dosing diary in which they will be required to record dosing dates and times. These diaries should be brought to each visit so that the study staff may check compliance. At the end of the study, the dosing diaries will be retained in the patient's file as source documentation.

CONFIDENTIAL PROTOCOL

An Open Label, Safety Study to Assess the Potential for Adrenal Suppression Following Maximal Use Treatment with Desoximetasone 0.25% shampoo(Taro Pharmaceuticals U.S.A., Inc.) in Patients with Scalp Psoriasis

At Visit 1 qualified study patients will be provided with one 120 ml bottle of desoximetasone 0.25% shampoo along with instructions for dosing. This bottle should be weighed before dispensing and the weight recorded. At Visit 2, the bottle should be collected and weighed and a new 120 ml bottle of shampoo should be weighed and dispensed along with dosing instructions. This bottle will be returned and weighed at Visit 3.

Treatment compliance will be encouraged by instructing the patient on the proper dosing technique and by the use of the daily diary. Compliance will be assessed by evaluation of the diary.

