9.5 Study Conduct

The cortisol response test is to be done in the morning as the body's peak cortisol level is directly related to the event of awakening. Visit 1 and Visit 3 should be scheduled before noon and subjects should not apply the study drug within 12 hours of Visit 3.

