9.6.18 Cortisol Response Test

At Visit 1 and Visit 3 all patients will have a cortisol response test performed according to the procedure detailed in Appendix D. The resulting blood sample should be sent to ACM Global Laboratory for immediate testing.

The test at the End of Study visit should not be performed if the patient dosed within 12 hours.

A patient will be considered to have normal basal cortisol level and adrenal function if they meet all three criteria listed below under Normal. Failure to meet any of these criteria is indicative of abnormal adrenal function or potential HPA axis suppression, even in absence of related symptoms (e.g. nausea, headache, myalgia, fatigue or loose stool); for abnormal results, the patient will be monitored in accordance to the follow-up schedule below.

	Cortisol Results	
	Normal	Abnormal
Basal (pre Cortrosyn™ injection)	≥ 5 mcg/100ml	< 5 mcg/100ml
30 minutes post	≥ basal value + 7	< basal value + 7

CONFIDENTIAL PROTOCOL

An Open Label, Safety Study to Assess the Potential for Adrenal Suppression Following Maximal Use Treatment with Desoximetasone 0.25% shampoo(Taro Pharmaceuticals U.S.A., Inc.) in Patients with Scalp Psoriasis

Cortrosyn™ injection	> 18 mcg/100ml	≤ 18 mcg/100ml
----------------------	----------------	----------------

HPA Axis suppression will be defined as a 30 minute post Cortrosyn™ injection level cortisol level of ≤ 18 mcg/100ml. If the Visit 1 Cortisol Response Test shows signs of HPA axis suppression as defined above the patient will be contacted and instructed to discontinue the use of study product, not to initiate any new steroid therapy, topical or otherwise and an End of Study Visit will be scheduled to conduct a Cortisol Response Test at least 28 days after the initial Cortisol Response Test at Visit 1 to assess for HPA axis suppression. At Visit 3 the study treatment period will be over, any patients with results of HPA axis suppression will be advised not to initiate any new steroid therapy, topical or otherwise, and to return to the site in 28 days at which time they will be assessed for HPA axis suppression.

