Any patient presenting with symptoms of HPA axis suppression, such as nausea, headache, myalgia, fatigue or loose stool, will be referred to an endocrinologist. As an additional safety precaution, wristbands identifying the patient as someone suffering from adrenal suppression secondary to steroid withdrawal will be provided to alert medical personnel should any emergencies arise before adrenal function returns to normal.

If the results of the cortisol response test still show signs of HPA axis suppression 28 days after discontinuing therapy the patient will be asked to return in 28 days (56 days after discontinuing steroid therapy) for another follow-up test. If the patient is still showing signs of HPA axis suppression 56 days after discontinuing steroid therapy and presents with related symptoms, the patient will be referred to an endocrinologist.

If HPA axis suppression persists for 56 days after discontinuing steroid therapy, but the patient has no symptoms they will be asked to return in 28 days (84 days after discontinuing steroid therapy) for another follow-up test. If HPA axis suppression persists for 84 days after discontinuing steroid therapy the patient will be referred to an endocrinologist regardless of symptoms.

Patients should not be subjected to Cortrosyn™ testing, or any other challenge to their adrenal response, any sooner than 4 weeks from their last Cortrosyn™ test.

Follow-Up Schedule for Patients showing signs of HPA Axis Suppression

Days after d/c	HPA Results	Symptoms	Patient Course
28	Normal	N/A	Study over
28	Abnormal	Yes	Refer to endocrinologist
28	Abnormal	No	Repeat test in 28 days
56	Normal	N/A	Study over
56	Abnormal	Yes	Refer to endocrinologist
56	Abnormal	No	Repeat test in 28 days
84	Normal	N/A	Study over
84	Abnormal	Yes or No	Refer to an endocrinologist

CONFIDENTIAL PROTOCOL

An Open Label, Safety Study to Assess the Potential for Adrenal Suppression Following Maximal Use Treatment with Desoximetasone 0.25% shampoo(Taro Pharmaceuticals U.S.A., Inc.) in Patients with Scalp Psoriasis

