10.1.2 Safety Analysis of Potential HPA Axis Suppression

Dosing will be once daily for 28 days. Patients with normal adrenal function at baseline, use at least 21 doses of the study product and have data from a post-treatment cortisol response test will be included in the analysis. Patients who have not used 21 doses of the study product will be excluded from the primary analysis of HPA axis suppression.

The primary analysis of interest is to assess the proportion of patients considered to have demonstrated possible HPA axis suppression following treatment with the study medication. As a secondary analysis of the data a logistic regression of the proportion of patients in the study with HPA axis suppression will be performed with % scalp affected as a covariate. See Appendix D for results from the cortisol response test considered indicative of potential HPA axis suppression.

For all patients the actual amount of desoximetasone (mg) applied during the study will be calculated from recorded bottle weights and presented.

After the completion of 5 patients an interim analysis will be performed and presented.

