5. STUDY ENDPOINTS AND ANALYSIS POPULATIONS

Primary Outcome Measures:

Hypothalamic Pituitary Adrenal (HPA) Axis Response to Cosyntropin demonstrating the absence or presence of adrenal suppression at the end of treatment defined by the following criteria: 30 minute post Cortrosyn™ injection level cortisol level of \leq 18 mcg/100ml during the Cortisol Response Test.

The primary endpoint is the proportion of patients in the study with HPA axis suppression following treatment with the study medication.

Safety Population:

Safety Population includes all patients who applied at least one dose of study drug.

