6.2 Statistical Analyses

6.2.1 Safety Analysis of Potential HPA Axis Suppression

Dosing will be once daily for 28 days. Patients who have normal adrenal function at baseline, use at least 21 doses of the study product and have data from a post-treatment cortisol response test will be included in the analysis.

The primary analysis of interest is to assess the proportion of patients considered to have demonstrated possible HPA axis suppression following treatment with the study medication.

A logistic regression of the proportion of patients in the study with HPA axis suppression may be performed as exploratory analysis with % scalp affected as a covariate. This will depend on the distribution of the % scalp data collected. See Appendix D for results from the cortisol response test considered indicative of potential HPA axis suppression.

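### Two end points for dosing and no maximum dose-to-test interval leave time off drug at the primary cortisol test uncontrolled when Visit 3 falls on Days 30-31

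*Protocol*

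**What the plan says.** Protocol 9.4.1 contains two statements on how long to dose. The first tells patients to "apply the study product to psoriasis-affected areas of the dry scalp once daily for 28 days". The next paragraph says "The patient will be instructed to apply the medication once daily until" the next scheduled visit, which after Visit 2 is Visit 3. Visit 3 is set for Day 29 ± 2 (Protocol 9.5.3), so Days 27-31.

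The timing of the last dose before the test is limited on one side only. Protocol 9.5 says "subjects should not apply the study drug within 12 hours of Visit 3", and Protocol 9.6.18 and Appendix D say "The test at the End of Study visit should not be performed if the patient dosed within 12 hours". No maximum is given.

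Protocol 9.6.18 and Appendix D also rule out Cortrosyn testing, "or any other challenge to their adrenal response, any sooner than 4 weeks from their last" such test. The first test is at Visit 1, Day 1.

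SAP 5 defines the primary outcome as the response to cosyntropin "demonstrating the absence or presence of adrenal suppression at the end of treatment". For the analysis set, SAP 6.2.1 takes patients with normal adrenal function at baseline who "use at least 21 doses of the study product and have data from a post-treatment cortisol response test will be included in the analysis". Protocol 10.1.2 adds: "Patients who have not used 21 doses of the study product will be excluded from the primary analysis of HPA axis suppression". Neither text has a condition on when the last dose was taken.

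The nearest thing to an upper limit is a category in SAP shell T16.1.9.2. It counts as a deviation that product was not used about 24 hours before a clinic visit.

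**The concern.** The study asks whether the axis is suppressed at the end of maximal use. If some patients are tested the morning after their last dose and others two or three days later, T16.1.9.4 pools tests that do not measure the same thing. Protocol 7.3 describes recovery after withdrawal as usually rapid, so extra time off drug would more likely hide suppression than create it. In a steroid safety study in 12-17-year-olds, that is the unsafe direction.

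The plan also does not agree with itself. A patient who takes all 28 doses on Days 1-28 and attends inside the window on Day 31 has followed the 28-day instruction, yet fits the SAP's 24-hour deviation category. No protocol instruction stands behind that category, and it plays no part in the primary analysis.

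**Working it through.** **Inputs from the documents.** Once-daily dosing and 28 expected doses (Protocol 9.1). Visit 3 on Days 27-31, before noon (9.5, 9.5.3). At least 12 hours from dose to test (9.5, 9.6.18). Four weeks between Cortrosyn tests (9.6.18). At least 21 doses for the primary set (SAP 6.2.1).

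**Assumptions.** First dose on Day 1, when product is dispensed. Dose at 09:00 or 21:00, test at 09:00.

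**The plan's own figure.** Daily doses from Day 1 to Day 28 give 28 doses, as stated. As a cross-check, the Visit 4 call on Day 42 is about 14 days after dosing ends (9.5.4), and 42 - 14 = Day 28.

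**Time off drug at the test.** A morning test with a 12-hour minimum puts the last dose no later than the day before. So the last dosing day is the smaller of 28 and (visit day - 1) under the 28-day phrase, and visit day - 1 under the until-visit phrase. The interval is (visit day - last dosing day) days after a 09:00 dose, and half a day less after a 21:00 dose.

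| Visit 3 | 28-day phrase: doses, days off | Until-visit phrase: doses, days off |
|---|---|---|
| Day 27 | 26, 0.5-1 | 26, 0.5-1 |
| Day 28 | 27, 0.5-1 | 27, 0.5-1 |
| Day 29 | 28, 0.5-1 | 28, 0.5-1 |
| Day 30 | 28, 1.5-2 | 29, 0.5-1 |
| Day 31 | 28, 2.5-3 | 30, 0.5-1 |

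The phrases therefore differ only on Days 30-31: 1.5-3 days against 0.5-1 day.

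**Sensitivity to the first dose.** If the first dose is on Day 2, the 28th falls on Day 29 and the phrases differ only on Day 31 (1.5-2 days against 0.5-1).

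**Four-week rule.** Day 1 + 28 days = Day 29. A test on Day 27 comes after 26 days and one on Day 28 after 27 days, so both break the rule. Days 29, 30 and 31 are the only days in the window that respect it, and the phrases conflict on two of those three.

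**Does dosing to the day before Visit 3 fit the other limits?** On Days 29-31 it gives 28-30 doses. Against 28, 29/28 = 103.6% and 30/28 = 107.1%, inside the 21-35 dose limits of Protocol 9.6.15. Fourteen days after a last dose on Days 28-30 is Days 42-44, inside Day 42 ± 4. The longest interval with a dose on the calendar day before is 00:00 to noon the next day, 36 hours.

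**The case against.** The best reply is that the two phrases can be reconciled. A 28-dose course is stated throughout, the Day 42 call points to dosing that ends on about Day 28, and dosing until the next visit can be read as the between-visit instruction in a study that checks diaries and exchanges bottles visit by visit. This is a fair reading, and it makes the gap look like an ordinary effect of a ± 2 day window. It does not remove the gap, because a course capped at 28 doses is the very reading that gives 1.5-3 days off drug on Days 30-31.

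It can also be said that the interval is recoverable. The diary records dosing dates and times, L16.2.5.1 lists the last-dose date, and L16.2.6.1 lists the test date. With 5-10 patients, a reader can work out each gap in days. That stands and keeps the issue small, but it reports the spread without preventing it.

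The third reply is that no material effect is shown. This also stands. The only dated recovery in the documents is in the spray study (Protocol 7.3), where all 3 suppressed patients of 21 were normal at the first follow-up, 28 days after treatment. The retest schedule runs at 28, 56 and 84 days. Nothing shows what one or two extra days do to a result near 18 mcg/100 ml.

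A reader might infer more than the documents support:

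- **That two thirds of patients are affected.** This needs visits spread evenly over Days 29-31. Day 29 is the target, and the share is not given.
- **That tests 7.5-10 days off drug are to be expected.** The 21-dose rule would admit doses on Days 1-21 with a test on Day 29 (7.5-8 days) or Day 31 (9.5-10 days). But every missed dose would have to fall at the end, and Visit 2 provides diary review and counselling. The two phrases do not cause this case.
- **That the primary proportion is biased by 10-20 points.** One changed result is 1/5 = 20 points or 1/10 = 10 points, but that holds for any single misclassification. It measures the small sample, not this problem.

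**Conclusion.** The concern holds, at minor to moderate severity. With a Day 1 first dose, the plan followed as written allows the primary test at about 1.5-3 days off drug for Visit 3 on Days 30-31, where the other instruction in the same section would give 0.5-1 day. No maximum interval limits this in either document. Separately, Days 27-28 of the Visit 3 window conflict with the four-week Cortrosyn rule.

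The likely direction is towards missed suppression, on the premise that adrenal function begins to recover once dosing stops. The size cannot be derived from the documents and is probably modest. The case for acting is that a single dosing and timing rule restores the meaning of the primary outcome cheaply. It does not rest on a demonstrated bias.

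**What to change.** 1. In Protocol 9.4.1 use one instruction: *once daily from Day 1 through the day before Visit 3*. Hold the scheduled Visit 3 test on Day 29 + 2, with Day 29 as the target. State expected doses as 28-30 wherever 28 is given.
2. In Protocol 9.5, 9.6.18 and Appendix D keep the 12-hour minimum and add that the last dose should be on the calendar day before the test, at most 36 hours before it. A later test is still done and is logged as a deviation.
3. In SAP T16.1.9.2 replace the 24-hour category with one for a last dose not taken 12-36 hours before the Visit 3 test.
4. In SAP 6.2.1 keep all eligible patients in the primary proportion. Add one row to T16.1.9.4 with the same count for patients whose last dose was on the calendar day before the test. The dates needed are already listed in L16.2.5.1 and L16.2.6.1.

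Leave the 21-35 dose limits, the denominator of 28 and the 21-dose analysis rule as they are, since 29-30 doses lie within them. Scaling the limits would raise the 75% floor to 22 of 29 (21.75) or 23 of 30 (22.5). A patient with 21 doses (72.4% or 70.0%) would then be non-compliant yet still in the primary set.

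Cost: at most two extra doses of a potent corticosteroid per patient (30 against 28, +7.1%), which the until-visit phrase already requests; a window with no early days; and a minor IRB-approved amendment with matching SAP edits. Supply should be checked. If Visit 2 is on Day 12, the second 120 ml bottle must cover up to 19 doses (120/19 = 6.3 ml each) instead of 17 (120/17 = 7.1 ml), and no volume per dose is stated. Testing on Day 29 only would avoid the extra doses, but a one-day window would itself produce out-of-window tests.

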9.4.2 Identity of Investigational Product

Desoximetasone 0.25% shampoo, w/w will be used in this study

9.4.3 Method of Assigning Patients to Treatment Groups

Patients will be assigned to the treatment in an open label fashion.

9.4.4 Packaging

This is an open-label study. The study product will contain a label with the following information:

- Protocol number
- Bottle number
- Space for patient number, patient's initials and dispensed date
- A note that the drug is for Investigational Use Only

9.4.5 Accountability

The Investigator or designee will maintain an inventory of all study product supplies received.

9.5 Study Conduct

The cortisol response test is to be done in the morning as the body's peak cortisol level is directly related to the event of awakening. Visit 1 and Visit 3 should be scheduled before noon and subjects should not apply the study drug within 12 hours of Visit 3.

9.5.1 Visit 1: Screening/Enrollment (Day 1), before 12 pm

1. **Informed Consent/Accent:** Patients who are willing to comply with study procedures will read and sign the assent form. The parent or legal guardian should sign the consent form and the child will be required to sign a patient "assent" form that will be written in such a way as to be understandable to a child.
2. **Medical History and Demographics:** Review the patient's demographic and medical history including concomitant medication use within the last 12 weeks.
3. **Physical Examination:** A general physical exam will be conducted.
4. **HEENT Examination:** A general exam of the head, eyes, ears, nose and throat will be conducted at the clinic.

CONFIDENTIAL PROTOCOL

An Open Label, Safety Study to Assess the Potential for Adrenal Suppression Following Maximal Use Treatment with Desoximetasone 0.25% shampoo(Taro Pharmaceuticals U.S.A., Inc.) in Patients with Scalp Psoriasis

5. **% Scalp Affected:** Patient's scalp will be examined by Investigator/designated clinician to determine the percent surface area affected with plaque psoriasis. Refer to Appendix B.
6. **Vital Signs:** The patient's vital signs will be recorded (pulse, blood pressure, temperature and respiration rate).
7. **Pregnancy Test:** A pregnancy test will be required of all females of child bearing potential prior to enrollment.
8. **Investigator's Global Assessment:** Patient's scalp will be examined to determine a psoriasis severity score based on a global assessment of plaque elevation, scaling and erythema by the Investigator/designated clinician (refer to Appendix A). Patients with a score of 3 or more, indicating moderate to severe psoriasis will be included in the study.
9. **Concomitant Medication:** Review with the patient use of concomitant medication within the last 12 weeks.
10. **Confirm Inclusion/Exclusion Met:** Confirm the patient meets all inclusion/exclusion criteria.
11. **Laboratory Evaluations:** A blood sample will be collected for hematology and clinical chemistry testing. (See Appendix F).
12. **Cortisol Response Test:** All patients will have a cortisol response test performed according to the procedure detailed in Appendix D.
13. **Dispense Study Product:** If patient is eligible to enroll, record the weight of one bottle of study product and dispense with instructions.
14. **Provide Dosing Diary:** Provide diary and instruct patient regarding how it is to be filled out and how study product is to be used.
15. **Provide Patient Wristband:** Each patient will receive a wristband to indicate that the patient is using a medication that has the potential to cause HPA axis suppression.
16. Schedule Visit 2.

